### **6.1. Dose modification and toxicity management**

#### **6.1.1. Radiotherapy**

Patients who, for reasons unrelated to toxicity, discontinue radiotherapy for more than 2 weeks will be excluded from the study. In the case of interruptions of less than 2 weeks, the patient will resume treatment from the point where he was interrupted.

**A severe toxicity (G3-4) related to radiotherapy or due to combination of the RT+durvalumab/tremelimumab, RT will be suspended until recovery to G1. However, if it is toxicity unrelated to the RT, it will continue without variations.**

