## **3. STUDY DESIGN**

### **3.1. Overview of study design**

This is an open-label, multicenter, phase II trial of the combination of durvalumab plus tremelimumab with concurrent normofractionated radiotherapy in patients with localized muscle invasive bladder cancer treated with a selective multimodality bladder conservative approach. The study will be conducted in a small group of centers with multidisciplinary teams with wide experience in multimodality bladder preservation therapy (7 centers belonging to SOGUG).

The treatment consisted of initial transurethral resection (TUR) of the tumor, with multiple random biopsies of normal-appearing bladder urothelium, followed by durvalumab 1500 mg i.v. plus tremelimumab 75 mg i.v., every 4 weeks for a total of 3

doses. Two weeks after the initiation of immunotherapy, normofractionated external-beam radiotherapy with high-energy photons will be started. Radiotherapy will be administered concurrently with immunotherapy at doses of 46 Gy to the minor pelvis and 64-66 Gy to the bladder. Six weeks after the end of radiotherapy as an efficacy determination, ALL patients will undergo a new cystoscopy with biopsies of the tumor bed and all residual present lesions. Response is defined as an absence of invasive cancer at post immunotherapy biopsy ( $\leq$ cT1). Patients with response to immunotherapy will be candidates to bladder preservation, whereas in those with residual muscle invasive tumor the possibility of salvage radical cystectomy must be evaluated. Patients developing an isolated bladder invasive relapse during follow-up will be also possible candidates to salvage cystectomy, whereas those developing a superficial relapse in the preserved bladder will be managed with TUR and intravesical BCG.

To monitor accurately the potential toxicity of radiotherapy associated with durvalumab and tremelimumab, an initial cohort of 5 patients of first Simon Optimax stage of 12 patients, will be treated. If no dose limiting toxicity is observed in  $\geq$ 2 of these patients in the 12 weeks of observation period, the rest of patients will be treated at full doses. In contrast, if severe toxicity is observed in  $\geq$ 2 of these patients, 3 additional patients will be treated. If dose limiting toxicity is seen in one of these additional patients, the therapeutic regimen will be modified in the subsequent ones, administering full doses of durvalumab but discontinuing tremelimumab after the first dose.

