#### **4.4. Withdrawal of patients from study treatment**

An individual patient will not receive any further investigational product if any of the following occurs:

- An individual patient will not receive any further durvalumab + tremelimumab combination therapy.
- Patient will not receive tremelimumab monotherapy in any case.
- Withdrawal of consent or lost to follow-up.
- Adverse event that, in the opinion of the investigator or the sponsor, contraindicates further dosing.
- Any AE that meets criteria for discontinuation, as defined in Section 10.
- Patient is determined to have met one or more of the exclusion criteria for study participation at study entry and continuing investigational therapy might constitute a safety risk.
- Consumption of illicit drugs or other substances by the patient which, at the discretion of the investigator, may reasonably contribute to the toxicity or otherwise, interfere in some with the results.
- Pregnancy (proof of beta-HCG compatible with pregnancy, communicating pregnancy as a serious adverse event), or intent to become pregnant.
- Grade  $\geq 3$  infusion reaction.
- Request to discontinue treatment by the patient or a legal representative.
- At the specific request of the sponsor and / or research coordinators of the trial.
- Patient noncompliance that, in the opinion of the investigator or sponsor, warrants withdrawal; e.g., refusal to adhere to scheduled visits.
- Initiation of alternative anticancer therapy including another investigational agent.
- Development of a secondary malignant tumor requiring treatment.
- Confirmation of PD and investigator determination that the patient is no longer benefiting from treatment with durvalumab + tremelimumab. Patients who are permanently discontinued from further receipt of investigational product, regardless of the reason (withdrawal of consent, due to an AE, other), will be identified as having permanently discontinued treatment

Patients who are permanently discontinued from receiving investigational product will be followed for safety per Section 10 and Appendix 1, including the collection of any protocol-specified blood specimens, unless consent is withdrawn or the patient is lost to follow-up or enrolled in another clinical study. All patients will be followed for survival. Patients who decline to return to the site for evaluations will be offered follow-up by phone every 3 months as an alternative.

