#### **4.5. Withdrawal of patients from study**

Criteria for withdrawal of the study:

1. Withdrawal of informed consent
2. Death of the patient
3. Loss of follow-up

The investigator will do everything possible to keep all patients in the study unless it is considered that the most appropriate option for the patient is to interrupt his/her participation.

If a patient refuses to continue his/her participation in the study, all end-of-study evaluations should be performed if the patient accepts or can be evaluated. The date and reason for withdrawal should be recorded in the eCRF.

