## **6. TREATMENT PLAN**

The treatment consisted of initial TUR of the tumor, with multiple random biopsies of normal-appearing bladder urothelium, followed by durvalumab 1500 mg i.v. plus tremelimumab 75 mg i.v., every 4 weeks for a total of 3 doses.

Two weeks after the initiation of immunotherapy, normofractionated external-beam radiotherapy with high-energy photons will be started. Radiotherapy will be administered concurrently with immunotherapy at doses of 46 Gy to the minor pelvis and 64-66 Gy to the bladder.

Six weeks after the end of radiotherapy, ALL patients will undergo a new cystoscopy with biopsies of the tumor bed and all residual present lesions as an efficacy determination. In patients with persistent prominent inflammatory reaction at this moment, the cystoscopy can be performed 1-2 weeks later (6 to 8 weeks after the end of radiotherapy). Response is defined as an absence of invasive cancer at post immunotherapy biopsy ( $\leq$ cT1). Patients with response to immunotherapy will be candidates to bladder preservation, whereas in those with residual muscle invasive tumor the possibility of salvage radical cystectomy must be evaluated. Patients developing an isolated bladder invasive relapse during follow-up will be also possible candidates to salvage cystectomy, whereas those developing a superficial relapse in the preserved bladder will be managed with TUR and intravesical BCG.

Patients will be followed up every 3 months the first year, every 4 months the second year and every 6 months thereafter with abdomen and pelvis CT scan, Rx thorax, urine cytology. Additionally of the mandatory efficacy cystoscopy and bladder biopsy (6w post RT), other cystoscopy and bladder biopsy will be performed in case of detection abnormalities in the cytology or imaging studies. The study will be closed 2 years after the last patient inclusion.

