### **8.1.5. Follow-up Visits**

All patients will be followed for survival until the end of the study regardless of further treatments, or until the sponsor ends the study. It is of special interest the long-term follow-up of survival, disease free survival and the preservation of the bladder free of tumor.

Given the potential risk for delayed immune-related toxicities, safety follow-up must be performed up to 90 days after the last dose of durvalumab and tremelimumab administration.

The extended safety follow-up beyond 30 days after last study drug administration may be performed either via a site visit or via a telephone call with subsequent site visit requested in case any concerns noted during the telephone call.

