#### 11.1.2. Efficacy analysis set

The efficacy analysis will be a *per protocol analysis*. The efficacy analysis set will include all patients who receive at least 2 cycles of durvalumab and 3 weeks of radiotherapy. The efficacy analysis set will be the primary population for evaluating treatment efficacy.

Additionally, intention to treat analysis will be performed for efficacy data.

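### Section 6.1.1 takes patients with a long non-toxic radiotherapy break off study and the replacement rule substitutes others, in conflict with the sections that keep all patients in for biopsy and survival

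*Combined protocol and SAP*

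**What the plan says.** Two rules in the treatment plan act on long radiotherapy breaks.

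- **Section 6.1.1:** "Patients who, for reasons unrelated to toxicity, discontinue radiotherapy for more than 2 weeks will be excluded from the study". The phrase about exclusion is not defined.
- **Section 6 (Replacement of patients), repeated in 6.1.2:** a patient who stops radiotherapy for more than 2 weeks is replaced. For this trigger, no distinction is made between toxicity and other reasons.

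The rest of the protocol keeps patients in.

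- **Section 4.5**, under "Criteria for withdrawal of the study", lists withdrawn consent, death and loss to follow-up. A radiotherapy break is not listed. It adds: "The investigator will do everything possible to keep all patients in the study", with an exception where stopping is judged best for the patient.
- **Section 4.4**, on patients who have stopped investigational product: "All patients will be followed for survival".
- **Section 8.1.5:** "All patients will be followed for survival until the end of the study regardless of further treatments".
- **Section 3.1**, and section 6 in near-identical terms, on the primary endpoint: "ALL patients will undergo a new cystoscopy with biopsies of the tumor bed and all residual present lesions".

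For the analysis, section 11.1.2 defines a per-protocol efficacy set that "will include all patients who receive at least 2 cycles of durvalumab and 3 weeks of radiotherapy". It has no criterion on breaks. It also promises an intention-to-treat (ITT) analysis, without defining that set.

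**The concern.** The protocol otherwise separates stopping treatment (4.4) from leaving the study (4.5). Section 6.1.1 merges the two, so a site can obey it literally only by departing from the sections that require biopsy and follow-up in everyone.

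The patients concerned can belong to the primary analysis. If such a patient leaves before the response cystoscopy, the primary outcome is missing, and events for bladder preservation, relapse and survival may go uncollected. The replacement rule then brings in another patient, and nothing says whether the 19 of 32 criterion in section 11.3 counts the first patient, the substitute or both.

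A second feature is that removal from the study depends on how the site labels the reason for the break. Two patients with the same exposure and the same gap are both replaced, but only the one whose gap is labelled non-toxic is excluded under 6.1.1. In an open-label single-arm trial decided on one count of responders, outcome collection should not rest on that label.

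**Working it through.** **1. Can a patient be in the efficacy set and then be excluded?**

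Section 6 starts radiotherapy two weeks after the first immunotherapy dose, that is, at the start of week 3. Three weeks of it end at the close of week 5. SAP Table 28 places the second durvalumab dose in week 5, so both conditions of 11.1.2 can be met at about the end of week 5. Section 1.3.3 gives 32 bladder fractions at 5 per week, and 32/5 = 6.4 weeks. That leaves 6.4 − 3 = 3.4 weeks of radiotherapy in which a disqualifying break can occur. The answer is yes. A break before that point affects only the ITT analysis.

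**2. Reproduce the plan's design.**

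Inputs from section 11.3: null response rate 0.5, target 0.7, 12 + 20 = 32 patients, type I error 0.10, power 80%. For stage 1 boundary *a* and final boundary *r*, the chance of a positive trial at response rate *p* is

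Pr(positive) = Σ (x = a to 12) Bin(x; 12, p) × Pr[Bin(20, p) ≥ r − x].

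A search over Simon designs gives the optimal one as 12 + 20 = 32, so the sample size reproduces. Its boundaries are at least 7/12 and at least 20/32, with type I error 0.0899 and power 0.8051. The boundaries as worded in section 11.3 (at least 6/12, 19/32) give type I error 0.1746 and power 0.9092. That mismatch with the planned 0.10 is a separate matter. It is stated here only because it sets the baseline, and both sets of boundaries are carried below.

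**3. Effect of the rules.**

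The documents give no frequency, so take a proportion *q* of patients affected, with *q* = 5% or 10% (assumed).

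(a) *Affected patients stay in the 32, have no biopsy and count as non-responders.* The effective rate is p(1 − q). For the target and q = 5% it is 0.7 × 0.95 = 0.665. For q = 10% it is 0.7 × 0.90 = 0.63.

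(b) *Affected patients are dropped and replaced.* If the rate over all enrolled patients is 0.5 and affected patients respond at rate *e*, the patients who remain respond at (0.5 − q·e)/(1 − q). For q = 5%:
- e = 0: 0.5/0.95 = 0.526
- e = 0.25: 0.4875/0.95 = 0.513
- e = 0.5: 0.475/0.95 = 0.500

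| | Boundaries as worded (6/12, 19/32) | Simon-optimal (7/12, 20/32) |
|---|---|---|
| Power, nobody affected | 0.909 | 0.805 |
| Power, (a), q = 5% | 0.823 | 0.681 |
| Power, (a), q = 10% | 0.700 | 0.533 |
| Type I error, nobody affected | 0.175 | 0.090 |
| Type I error, (b), q = 5%, e = 25% to 0% | 0.215 to 0.260 | 0.116 to 0.146 |
| Type I error, (b), q = 10%, e = 25% to 0% | 0.266 to 0.376 | 0.150 to 0.232 |
| Type I error, (b), e = 50% | 0.175 | 0.090 |

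The two ways of counting err in opposite directions, and the plan does not say which applies.

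**The case against.** The strongest reply is that the protocol nowhere says these patients lose their biopsy or follow-up. One undefined phrase in a dose-modification section stands against sections 3.1, 4.4, 6 and 8.1.5. Section 4.6 keeps survival follow-up even after consent to participation is withdrawn, unless that follow-up is itself refused. A site following those sections would collect everything. This stands: loss of data is the literal consequence of 6.1.1, not a stated instruction. It does not remove the conflict, because no passage says which text prevails.

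The list in 4.5 also should not be read as exhaustive. It does not call itself exclusive, it allows for stopping in the patient's interest, and section 8.3.5 ends participation when consent to donated samples is withdrawn. What can be said is that a radiotherapy break is not listed and that 4.5 asks for retention.

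A reader might infer that each excluded patient moves the response rate by 1/32, or 3.1 points. That does not follow. A patient who is replaced and dropped is outside the 32, and a patient kept alongside a substitute makes the denominator 33 or more.

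Nor do the documents show that the rule ever operated. SAP section 3.1 states that all 32 patients meet the safety and per-protocol conditions. The SAP shells list interruptions with duration, reason and restart, keep a row for cystoscopy not done, and have no category for exclusion. They cannot settle the matter either way, since they have no field for patients excluded or replaced outside the 32.

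Finally, a lower response rate in these patients is an assumption. Breaks for logistical reasons are also non-toxic and need not predict outcome.

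**Conclusion.** The conflict is real and should be resolved. Section 6.1.1 and the replacement rule cannot be applied literally alongside sections 3.1, 4.4, 4.5, 6 and 8.1.5, and they can reach patients who belong to the efficacy set and to any ITT set.

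The size is unknown. At an assumed 5% of patients, under the boundaries as worded, the cost is either power of 0.823 in place of 0.909, or type I error of 0.215 to 0.260 in place of 0.175. The second figure requires a response rate of 0 to 25% in those patients and disappears if their rate equals the null value of 0.5.

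The documents do not support the stronger statement that outcomes were lost or that the reported result is affected.

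**What to change.** 1. Reword 6.1.1 so that the break is recorded as discontinuation of radiotherapy, with the reason in the eCRF, and the patient stays on study for the response assessment and follow-up already required of all patients, unless a study-withdrawal criterion applies.
2. Reconcile the replacement rule in sections 6 and 6.1.2 with sections 4.4, 4.5, 6 and 8.1.5. State that such patients, replaced or not, remain in ITT, and in the efficacy set if 11.1.2 is met.
3. In sections 11.1.2 and 11.3, state which patients make up the 32 for the 19/32 rule when replacements have been enrolled.
4. If enrolment is complete, report how many patients were excluded or replaced under these rules, and their outcomes.

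The clinical handling of the break and the timing of the biopsy are left to the existing passages. The cost is wording in four or five places. No new visits or procedures are needed, because the cystoscopy and follow-up are already required of everyone. The response rate may come out slightly less favourable if these patients do respond less often.

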#### **6.1.2. Durvalumab and tremelimumab**

Guidelines for the management of immune-mediated reactions, infusion-related reactions, and non-immune-mediated reactions for durvalumab monotherapy and durvalumab + tremelimumab are provided in the Dosing Modification and Toxicity Management Guidelines in Appendix 1. Patients should be thoroughly evaluated and appropriate efforts should be made to rule out neoplastic, infectious, metabolic, toxin, or other etiologic causes of the imAE. Serologic, immunologic, and histologic (biopsy) data, as appropriate, should be used to support an imAE diagnosis. In the absence of a clear alternative etiology, events should be considered potentially immune related.

In addition, there are certain circumstances in which durvalumab and tremelimumab should be permanently discontinued (see Section 4.4 of this protocol and the Dosing Modification and Toxicity Management Guidelines in Appendix 1).

Following the first dose of IP, subsequent administration of durvalumab and tremelimumab can be modified based on toxicities observed as described in the Dosing Modification and Toxicity Management Guidelines in Appendix 1. These guidelines have been prepared by the Sponsor to assist the Investigator in the exercise of his/her clinical judgment in treating these types of toxicities. These guidelines apply to AEs considered causally related to durvalumab monotherapy and the durvalumab + tremelimumab regimen by the reporting investigator.

**Dose reductions are not permitted.** In case of doubt, the Investigator should consult with the Study Physician. In case of severe grade 3-4 toxicity, the possibility to discontinue tremelimumab, following the administration of durvalumab alone concurrently with radiotherapy, when the toxicity will recover, should be considered.

It is planned to replace those patients who interrupt the trial in advance (without having completed 12 weeks of treatment) and have not presented dose-limiting toxicity. Patients who have not been taking durvalumab and tremelimumab for more than 21 days or who discontinue treatment with radiotherapy for more than 2 weeks will also be replaced.

Patients should be thoroughly evaluated and appropriate efforts should be made to rule out neoplastic, infectious, metabolic, toxin, or other etiologic causes of the imAE. Serologic, immunologic, and histologic (biopsy) data, as appropriate, should be used to support an imAE diagnosis. In the absence of a clear alternative etiology, events should be considered potentially immune related.

All toxicities will be graded according to NCI CTCAE, Version 4.03 and RTOG/EORTC grading system.

## 7. RESTRICTIONS DURING THE STUDY AND CONCOMITANT TREATMENTS

### 7.1. Restrictions during the study

The following restrictions apply while the patient is receiving study treatment and for the specified times before and after:

#### *Female patient of child-bearing potential*

- Females of childbearing potential who are sexually active with a non sterilized male partner must use at least 1 highly effective method of contraception (Table 1) from the time of screening and must agree to continue using such precautions for 180 days after the last dose of durvalumab + tremelimumab combination therapy or 90 days after the last dose of durvalumab monotherapy. Non-sterilized male partners of a female patient must use male condom plus spermicide throughout this period. Cessation of birth control after this point should be discussed with a responsible physician. Not engaging in sexual activity for the total duration of the drug treatment and the drug washout period is an acceptable practice; however, periodic abstinence, the rhythm method, and the withdrawal method are not acceptable methods of birth control. Female patients should also refrain from breastfeeding throughout this period.

#### *Male patients with a female partner of childbearing potential*

- Non-sterilized males who are sexually active with a female partner of childbearing potential must use a male condom plus spermicide from screening through 180 days after receipt of the final dose of durvalumab + tremelimumab combination therapy or 90 days after receipt of the final dose of durvalumab

monotherapy. Not engaging in sexual activity is an acceptable practice; however, occasional abstinence, the rhythm method, and the withdrawal method are not acceptable methods of contraception. Male patients should refrain from sperm donation throughout this period.

- Female partners (of childbearing potential) of male patients must also use a highly effective method of contraception throughout this period (Table 1).

N.B Females of childbearing potential are defined as those who are not surgically sterile (i.e., bilateral tubal ligation, bilateral oophorectomy, or complete hysterectomy) or post-menopausal.

Women will be considered post-menopausal if they have been amenorrheic for 12 months without an alternative medical cause. The following age-specific requirements apply:

- Women <50 years of age would be considered post-menopausal if they have been amenorrheic for 12 months or more following cessation of exogenous hormonal treatments and if they have luteinizing hormone and follicle-stimulating hormone levels in the post-menopausal range for the institution or underwent surgical sterilization (bilateral oophorectomy or hysterectomy).
- Women ≥50 years of age would be considered post-menopausal if they have been amenorrheic for 12 months or more following cessation of all exogenous hormonal treatments, had radiation-induced menopause with last menses >1 year ago, had chemotherapy-induced menopause with last menses >1 year ago, or underwent surgical sterilization (bilateral oophorectomy, bilateral salpingectomy or hysterectomy).

Highly effective methods of contraception, defined as one that results in a low failure rate (i.e., less than 1% per year) when used consistently and correctly are described in Table 1. Note that some contraception methods are not considered highly effective (e.g., male or female condom with or without spermicide; female cap, diaphragm, or sponge with or without spermicide; non-copper containing intrauterine device; progestogen-only oral hormonal contraceptive pills where inhibition of ovulation is not the primary mode of action [excluding Cerazette/desogestrel which is considered highly effective]; and triphasic combined oral contraceptive pills).

